## **E. PROTECTION OF HUMAN SUBJECTS**

---

### **1. RISKS TO THE SUBJECTS**

#### **a. Human Subjects Involvement and Characteristics**

The PI and research staff have all completed the CITI Human Subjects Research Education Course and all other necessary human subjects training. A total of 110 male and female adult smokers, between 18 and 65 years old, will be enrolled in study procedures (considered enrolled when randomized to medication condition), primarily through media advertisements (i.e. internet, print, radio). We expect that we will need to consent more than 110 participants in order to enroll the estimated sample size for this study. Therefore, we expect to consent 150 participants, but expect 110 of those consented to qualify and be enrolled/randomized into the study.

We will aim to recruit 110 enrolled study participants to have sufficient power to detect between group differences, but will plan to over enroll (N=120 total participants) to account for data integrity issues in a small number of participants. Due to over enrolling, we will also expect to over-consent the proposed 150 and anticipate an increase to 180 consented participants. The inclusion/exclusion criteria are as follows:

#### **Inclusion Criteria**

1. Age 18-65
2. Daily smoker for  $\geq 6$  months, smoking approximately  $\geq 5$  cigarettes per day on average in the past month or must meet the criteria for nicotine dependence
3. Be interested in quitting smoking
4. Willing to engage in a 3-day quit attempt as part of study procedures
5. Willing to abstain from cannabis and other tobacco products during study procedures
6. If female, agreement to use birth control (any form) to avoid pregnancy during study procedures

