## **D. RESEARCH DESIGN AND METHODS (including data analysis)**

### Study Design

This study will assess NAC as both an initial cessation aid and relapse prevention aid. Interested individuals will receive a brief telephone screening to determine if they may be eligible to participate. They will then be scheduled for an initial assessment, consisting of informed consent, followed by completion of self-report questionnaires and semi-structured interviews to determine eligibility. If participants are eligible for the study, they will be asked to return for their training visit. At the training visit, participants will be given instructions on completing remote surveys and counseling in preparation for their target quit date (TQD). Participants will then return for their randomization visit (Day 0), which will occur within 30 days of screening. On Day 0, participants will be randomized to receive double-blind NAC or placebo for eight weeks. Urn randomization procedures will be used.

Participants will then be contingently reinforced for abstinence from smoking for three days while taking study medication. Following three days of reinforced abstinence, participants will complete the remaining 8-week treatment intervention. Medication will be terminated at the Week 8 end-of treatment (EOT) visit.

Participants will then return at Week 12 (Day 84) for 4-week post-treatment follow-up visit to assess smoking status. The study design is shown in Figure 1. If

participants have unexpected conflicts after randomization and cannot keep weekly visit schedule (i.e. transportation issues or visit activity during an extended holiday), then participants may be eligible to complete weekly visits remotely via telephone call. During remote visits, Participants will be called via phone and all protocol procedures will be completed with the exception of a CO sample. Biologic collection (i.e. urine sample) may be obtained with proper planning, the participant may be given the opportunity and supplies required to complete an offsite/at home urine collection should they be willing to follow the proper collection and storage of a sample. Participants will be assessed for AE's, medication compliance, and will complete emailed surveys all within the assigned visit window. A CO sample will be collected at the participants next in-clinic visit. This option will only be used as a last resort for uninterrupted study participation.

[figure not shown]

Figure 1. Study design

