### Assessment

Formal written consent will be obtained from all new participants enrolled in this project. Following the policies of the MUSC Institutional Review Board, written informed consent will be obtained and documented by approved research staff before any study-related procedures are performed. Informed consent will be obtained in a private research office. Each individual may take as much time as they like to decide if they do or do not wish to participate. Following informed consent, participants will complete self-report questionnaires, semi-structured interviews, a medical history, and will also be asked to provide breath and urine samples to assess smoking status, pregnancy status, and to screen for illicit drug use. [name] (PI) will review all screening material and, in consultation with [name] (Co-I and medical clinician) and/or other approved medical clinicians on this protocol, will determine study eligibility for each participant. Additionally, during the assessment visit, participants will be asked to sign a "lifestyle agreement" in which they agree to important aspects of the study procedures (e.g., abstaining from tobacco products and smoking cessation products, engaging in the 3-day quit attempt, and using some form of birth control [female participants only]). This agreement will help to promote adherence to study procedures and provide an additional opportunity to stress the importance of these protocol components. If participants remain interested in the study and meet eligibility criteria, they will be asked to complete morning report surveys through REDCap during the study. The morning report will ask about how many cigarettes were smoked the day prior, if alcohol and/or drugs were consumed, and time of medication dosing (added to survey after Randomization/Day0). Participants will be asked to begin completing morning reports following their screening visit. Links to access the morning report will be sent to participants through their mobile phone and their email address. Participants may complete morning reports on either their smartphone or on a computer.

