#### Randomization (Day 0)/Abstinence Period

Participants will return to the clinic on Day 0 to receive study medication. Participants will begin taking study medication on Day 1. Day 1 will also be when they abstain from smoking. Participants will be instructed to stop smoking no later than 11:59 pm on the night of their Day 0 visit. Participants will be reinforced contingently for abstinence from smoking on Days 1-3. Two breath CO samples per day will be taken remotely and videos will be submitted via REDCap surveys to confirm smoking status during that time (during Days 1-6 of the study). In order to monitor and confirm medication adherence during the first six days of the study, participants will also record themselves taking their morning and evening medication doses. These videos will be submitted via REDCap surveys at the same time as the CO samples are submitted. If the participant prefers to take the medication before the first prompt of the morning, they will be able to record their medication video and upload the file when completing the survey. Abstinence from smoking is defined as a breath CO of  $\leq$  6 parts per million (ppm) and/or a 50-75% reduction from the participant's average screening and Day 0 breath CO samples. Participants will continue to complete the morning reports through REDCap through the remainder of the study.

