#### Statistical Analyses

Categorical clinical and demographic variables will be assessed by chi-square tests of independence, while continuous variables will be assessed using Student's *t*-test. In addition to baseline group differences, preliminary analysis of baseline characteristics with tobacco use outcomes of interest will examine significant correlates of abstinence in the study population. Characteristics found to be significantly associated with tobacco abstinence and relapse outcomes will be included as covariates in the initial stages of model development. The primary measure of interest will be the proportion of biochemically confirmed and self-reported 3-day abstinence (defined as twice per day breath CO measures of  $\leq 6$  ppm or a 75% reduction from the participant's averaged baseline and Day 0 CO samples). The proportion of participants achieving 3-day abstinence will be compared between NAC and placebo treatment groups using logistic regression models (Specific Aim #1). Secondarily, there is great interest in determining if those who achieved 3-day abstinence under NAC treatment were less likely to relapse over the course of eight weeks compared than those who achieved abstinence under placebo treatment (Specific Aim #2). Daily smoking diary data will be used in conjunction with weekly breath CO measures to determine if and when relapse to regular smoking returned during the eight weeks of treatment with the study drug. Based on recommendations for defining treatment failure, relapse will be defined as smoking during seven consecutive days or smoking at least once over two consecutive weeks (54). This definition will account for regular and irregular smoking over the course of the eight-week intervention phase. Cox proportional hazards models will be developed to assess the efficacy of NAC in prolonging abstinence and preventing relapse. Additionally, end of study 7-day point prevalence abstinence will be assessed through the proportion of self-reported and biochemically confirmed 7-day abstinence. Biochemical confirmation for end-of-study abstinence is defined as a negative daily breath CO measures ( $\leq 6$  ppm or 75% reduction from baseline) and a negative urine cotinine measure ( $<80$  ng/mL). The main effect of NAC versus placebo on the proportion of abstinent participants will be assessed using logistic regression models. All stated models will be computed both unadjusted and adjusted for significant covariates and confounders found in the preliminary analysis. All randomized participants will be included in the primary analysis (intent-to-treat; ITT) and participants will be deemed not-abstinent at any missed visit or missing CO measure (drop-out/loss-to-follow up included). In addition to the primary ITT analyses,

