#### Nicotine withdrawal

This study involves a three-day period of abstinence. Participants will be asked to remain abstinent for a total of 72 hours. Participants will be daily smokers, and as such, they may experience tobacco/nicotine withdrawal symptoms and/or discomfort during this time. Tobacco withdrawal symptoms may include anxiety, depressed mood, irritability, restlessness, sleep difficulty and strange dreams, increased appetite/weight gain, headaches, tension, difficulty concentrating and general physical discomfort. There are no reports in the current literature of severe physiological or psychiatric consequences resulting from tobacco withdrawal. Participants will be informed of the potential discomfort they may experience during this brief period of abstinence and will be advised to contact research staff if they feel that their withdrawal symptoms worsen during the 72-hour period.

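### No breath-CO floor or still-smoking rule applies before randomization, so a participant already at or below 6 ppm can pass the primary CO test without any change

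*Combined protocol and SAP*

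**What the plan says.** **Entry.** Under Inclusion Criteria, the smoking requirement is daily smoking for six months or longer, at about five or more "cigarettes per day on average in the past month or must meet the criteria for nicotine dependence". Neither the inclusion nor the exclusion list contains a CO or cotinine threshold.

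**Screening.** Under Assessment, participants "will also be asked to provide breath and urine samples to assess smoking status, pregnancy status, and to screen for illicit drug use". No cut-off is attached. The principal investigator "will review all screening material and, in consultation with" a medical clinician decides eligibility. Morning reports of cigarettes smoked begin after this visit.

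**From screening to Day 0.** Study Design states: "Participants will then return for their randomization visit (Day 0), which will occur within 30 days of screening". The training visit in between includes counseling for the quit date. On timing of the quit, the Randomization (Day 0)/Abstinence Period section states: "Participants will be instructed to stop smoking no later than 11:59 pm on the night of their Day 0 visit". Study drug starts on Day 1.

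**Day 0 measurements.** The Smoking Assessments list schedules a cigarette diary, breath CO and an instant cotinine dipstick at Day 0. The only stated use of the Day 0 CO value is as part of the reference for the percentage-reduction limb of the abstinence test, "75% reduction from the participant's averaged baseline and Day 0 CO samples".

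**Endpoint.** Under Statistical Analyses, the primary measure is "biochemically confirmed and self-reported 3-day abstinence (defined as twice per day breath CO measures of" 6 ppm or less, or the 75% reduction. A missing CO reading counts as not abstinent.

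**The concern.** The 6 ppm limb is absolute. It shows that someone has stopped smoking only if that person would have been above 6 ppm while smoking. Nothing at entry secures this, so two kinds of participant can be counted as initial cessation without having quit on treatment:

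- **A light smoker whose usual CO is 6 ppm or less.** All six readings on Days 1 to 3 can pass while smoking continues. The biochemical check then adds nothing, and only self-report can show the smoking.
- **A smoker who stopped between screening and Day 0.** This person can meet both the CO and the self-report parts, although cessation came before the first dose.

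Aim 1 asks whether NAC helps smokers achieve three days of abstinence. Neither case is evidence of that. Both can raise the success rate in each arm and shrink the contrast. Both can also enter the abstainer subset for the Aim 2 relapse comparison.

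**Working it through.** **Step 1: entry rule against endpoint.** All four profiles below can be randomized under the written criteria.

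| Profile | CO test, Days 1-3 | Self-report | Full endpoint |
|---|---|---|---|
| Usual CO at or below 6 ppm, smokes and says so | can pass | fails | not met |
| Usual CO at or below 6 ppm, smokes and does not say so | can pass | passes | met, without abstinence |
| Stopped before Day 0, stays abstinent | passes | passes | met, but quit preceded drug |
| Stopped before Day 0, resumes on Days 1-3 | may fail | fails if reported | may not be met |

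The second and third rows are the problem.

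**Step 2: dilution.** Inputs from Power and Sample Size: 55 per arm, and the low scenario of 30% (placebo) and 50% (NAC) attaining three-day abstinence. The share *s* of participants counted abstinent regardless of arm is not in the documents; 5%, 10% and 20% are assumed. Each arm's rate becomes *s* + (1 − *s*)*p*, so the difference becomes (1 − *s*) × 20 points.

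| *s* | About how many per arm (55*s*) | Placebo | NAC | Difference |
|---|---|---|---|---|
| 0 | 0 | 30.0% | 50.0% | 20 points |
| 5% | 3 | 0.05 + 0.95 × 0.30 = 33.5% | 0.05 + 0.95 × 0.50 = 52.5% | 19 points |
| 10% | 5 to 6 | 37.0% | 55.0% | 18 points |
| 20% | 11 | 44.0% | 60.0% | 16 points |

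**Step 3: power.** The plan claims 80% power for differences as low as 20 points and gives no placebo rate. Assuming a two-sided 5% test, with *d* the difference and *p̄* the mean of the two rates:

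power = Φ{[*d*√55 − 1.96√(2*p̄*(1 − *p̄*))] / √(*p*₁(1 − *p*₁) + *p*₂(1 − *p*₂))}

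This gives 85% at 5% versus 25%, 75% at 10% versus 30%, and 57% at 30% versus 50%. So 80% is reached only at extreme placebo rates. That shortfall is a separate matter and is not caused by the entry rule. Starting from the plan's own scenarios:

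| Scenario | *s* = 0 | 5% | 10% | 20% |
|---|---|---|---|---|
| 30% vs 50% | 57% | 52% | 47% | 39% |
| 50% vs 75% | 78% | 75% | 71% | 63% |

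**Step 4: the other reading of the planning rates.** The 30% and 50% are stated for all those randomized, so they may already include such people. The same formula then runs backwards: the difference needed among the remaining participants is 20/(1 − *s*), which is 21.1, 22.2 or 25.0 points for *s* = 5%, 10% or 20%.

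**The case against.** The case for leaving the plan alone has several sound parts.

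- **Smoking status is measured before randomization.** A reader might infer from the missing rule that nobody looks. In fact the diary, CO and cotinine dipstick are all scheduled at Day 0. What is missing is a stated pass/fail use of them.
- **Participants are described as current smokers.** The Nicotine withdrawal section says: "Participants will be daily smokers, and as such, they may experience tobacco/nicotine withdrawal symptoms". Entry requires daily smoking, and Day 1 is the planned first day of abstinence. The Day 0 night instruction is a deadline; it does not invite earlier quitting, though it does not bar it. How far the dependence alternative in the criterion admits lighter smokers depends on how its wording is read.
- **The CO test is not the whole endpoint.** Self-report and complete readings are also required, so a low-CO smoker who reports smoking fails.
- **Low Day 0 CO does not fix the outcome.** An early quitter can resume on Days 1 to 3, and NAC might affect that. One low reading proves neither a low usual CO nor a quit.
- **Payment.** A reader might infer that self-report alone earns the $40 per day. The documents say only that payment depends on abstinence, and the Abstinence Period section defines abstinence by CO.
- **Aim 2.** Someone already abstinent at first dose is relevant to relapse prevention, which is where the background section expects NAC to work.
- **Existing analyses.** Modified-ITT and per-protocol analyses are planned and could carry a low-CO exclusion.

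These points limit the size of the concern and argue against excluding anyone on a single low Day 0 reading. They do not supply the missing rule, and the exploratory analyses as written do not mention Day 0 CO.

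**Conclusion.** The gap is real and worth closing. No CO floor applies at entry, the available Day 0 data do not gate randomization, and the absolute 6 ppm limb can be passed with no change from the starting value. Such people can be randomized; the documents do not show that any are, or how many.

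The loss of 1 to 4 points from a 20-point difference rests on an assumed 5% to 20% share, with every such participant scored abstinent in both arms. It is therefore an upper case for each share.

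A reader might also infer that the result would favor NAC. The documents do not support that: randomization balances these participants on average. The expected harm is a diluted contrast and an endpoint that partly measures something other than quitting on treatment.

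**What to change.** 1. **Eligibility.** Require screening breath CO above 6 ppm, matched to the endpoint cut-off. At Day 0, before randomization, confirm from the morning reports and CO already collected that the participant is still smoking. If the Day 0 data do not confirm this, allow a repeat within the existing 30-day window; do not exclude on one low reading.
2. **Analysis.** Prespecify a sensitivity analysis of Aim 1, and of the Aim 2 abstainer comparison, excluding participants with Day 0 CO at or below 6 ppm. This also covers anyone already randomized. The value precedes randomization, so the Aim 1 comparison stays randomized. The Aim 2 subset remains selected after randomization, as already planned.

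**Cost.** A short amendment using measurements already taken. A few very light smokers and early quitters would not be randomized, which narrows the population slightly. Slightly more screening may be needed within the planned 150 to 180 consents.

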#### **Exclusion Criteria**

1. Any serious or unstable medical/psychiatric disorder (including severe substance use disorders, other than tobacco use disorder) in the past month that may interfere with study performance based on PI judgment
2. Current pregnancy or breastfeeding
3. Current use of medications with smoking cessation efficacy
4. Known hypersensitivity to NAC
5. Use of carbamazepine or nitroglycerin (or any other medication deemed to be hazardous if taken with NAC) within 14 days of study participation.

### Targeted/Planned Enrollment Table

Total Planned Enrollment: 120participants

TARGETED/PLANNED ENROLLMENT: Number of Subjects			
Ethnic Category	Sex/Gender		
	Females	Males	Total
Hispanic or Latino	3	3	6
Not Hispanic or Latino	45	69	114
Ethnic Category: Total of All Subjects*	120		
Racial Categories			
American Indian/Alaska Native	0	0	0
Asian	1	1	2
Native Hawaiian or Other Pacific Islander	0	0	0
Black or African American	12	19	31
White	31	48	79
2 or more races	1	1	2
Racial Categories: Total of All Subjects*	45	69	114

Given the NIH definition of children as all individuals below age 18, this study will exclude children. Males and females will be included.

#### b. Sources of Materials

Research materials obtained from the individual participants include psychiatric and medical diagnoses information, expired air breathalyzer CO tests, urine pregnancy tests (females only), urine drug screen, blood pressure, pulse, craving, and adverse event information. Responses to questionnaires and expired breath CO measures will be submitted remotely through the participant's mobile phone (or loaner mobile phone) and uploaded directly into REDCap. Video capture of participant's breath CO samples and their surrounding area will also be captured remotely. Videos and images of participants will be stored within REDCap, which is a secure, password-protected data management system maintained by MUSC. For data back-up purposes, videos and participant images will also be stored on secured, password-protected servers maintained by the Addiction Sciences Division at MUSC. These files will only be accessed by the PI and designated research staff. Those files will not be linked with the participant's name, but will have their image, surrounding areas, and any other individuals captured within the frame. All precautionary measures will be taken to ensure that data files are not compromised and are available only for the PI and designated research staff to view. Research data will be obtained specifically for research purposes. We will not use existing specimens, records or data.

#### c. Potential Risks

##### Adverse events related to study medication

The informed consent process will be used to thoroughly educate participants about potential medication-related risks. Rigorous screening procedures and exclusion criteria are designed to exclude potential participants at elevated risk for adverse events. Specifically, study research staff will carefully assess adverse events with participants at each study visit and will contact the medical clinician immediately with any concerns. Research staff will also review the participant-completed Beck Depression Inventory at each visit. If the BDI results suggest deterioration with depression or other psychiatric conditions, a more comprehensive assessment will be completed, with careful plan to address symptoms (e.g., discontinuation of study medication if indicated, referral for psychiatric treatment if indicated, development of safety plan if indicated, etc.). The study PI and medical clinician will be immediately contacted in the event of acute concerns and will guide the plan for addressing and managing presenting symptoms. Participants will have access to the study physician 24 hours, 7 days a week for emergencies. Participants experiencing intolerable adverse events will have the opportunity to reduce dose or discontinue medication altogether, while remaining in the study for ongoing monitoring. Urine pregnancy tests will be conducted weekly throughout treatment for female participants.

Though detailed safety plans are in place for study participants, no serious or severe adverse events or

interactions are expected to occur with NAC. Adverse events related to this medication (e.g., allergic reaction, decreased appetite, gastrointestinal discomfort) are possible and will be assessed carefully throughout the study.

